## 12. QUALITY CONTROL AND QUALITY ASSURANCE

Site monitoring will be conducted to ensure that human subject protection, study procedures, lab procedures, study intervention administration are performed to comply with pertinent regulations, sponsor requirements, and GCP/ICH guidelines, and in accordance with the site and sponsor SOPs. DAIT, NIAID, or a designee will conduct site monitoring visits related to the protocol procedures and GCP standards.

## 12.1 Compliance, Access, Entry and Handling of Study Data

The site PI is required to keep accurate records to ensure that the conduct of the study is fully documented, and to ensure that CRFs are completed for all subjects according to study guidelines outlined in the study protocol and the Data System Users Instruction Manual.

Access to the data entry screens will be user ID and password protected. Each user will be provided with a unique personal ID and password. The investigational site participating in this study will maintain the highest degree of confidentiality permitted for the clinical and research information obtained from the subjects in this clinical trial. Medical and research records should be maintained at each site in the strictest confidence. However, as part of the quality assurance and legal responsibilities of an investigation, the investigational site must permit authorized representatives of the sponsor(s) and health authorities to examine (and when required by applicable law, to copy) clinical records for the purpose of quality assurance reviews, audits, and evaluations of the study safety and progress. Unless required by the laws that permit copying of records, only the coded identity associated with documents or with other subject data may be copied (and all personally identifying information must be obscured). Authorized representatives as noted above are bound to maintain the strict confidentiality of medical and research information that is linked to identified individuals. The investigational site will normally be notified before auditing visits occur.

All data will be entered, stored, and managed in a relational database supported by database servers at the DCC. The results of all clinical and laboratory evaluations will be maintained in the subjects' medical records and the data will be transferred from these source documents directly to the electronic study CRFs. In order to maintain security, all data will be encrypted using the Secure Sockets Layer protocol. This protocol allows an encrypted link to be established between the DCC web server and the computer at each center. In addition, the data will be verified by a series of computerized edit checks, and all relevant data queries will be resolved regularly. All discrepancies will be reviewed, and any resulting queries will be resolved with the site personnel and amended in the database.

All changes made to CRFs will be recorded in an electronic audit trail to allow all data changes in the data system to be monitored and maintained in accordance with federal regulations. Once a CRF is entered into the database and the person entering the data indicates that CRF is complete, any change to that data will be entered into the system's audit trail. The audit trail will record the CRF and variable that is changed, the old value, the new value, the date and time the change was made, reason change was made, and the user ID of the person making the change. Once a change is completed, the data system will re-validate all variables on that CRF. The changed CRF will be required to pass all validity and logic consistency checks. If any edit

criteria fail, the system will generate appropriate queries. The clinical center coordinator will be asked to resolve the questions before the changes are completed.

The change system will allow certified DCC personnel and certified clinical center coordinators to make changes. Changes can be initiated by DCC monitors, DCC coordinators, and certified site personnel. Site personnel can access only the data for their own center. The system will generate weekly summary listings of all changes made to the database, the person making each change, and the reason for each change. These reports will be carefully reviewed by the DCC coordinator to monitor for unnecessary changes and/or problems with the data system.

# 13. ETHICAL CONSIDERATIONS AND COMPLIANCE WITH GOOD CLINICAL PRACTICE

## 13.1 Statement of Compliance

This clinical study will be conducted using cGCP, as delineated in *Guidance for Industry: E6 Good Clinical Practice Consolidated Guidance* , and according to the criteria specified in this study protocol. Before study initiation, the protocol and the informed consent documents will be reviewed and approved by an appropriate EC or IRB, and NIAID/NIDDK. Any amendments to the protocol or to the consent materials must also be approved by the IRB/EC and submitted to the applicable Health Authorities before they are implemented.

## 13.2 Informed Consent and Assent

The informed consent form is a means of providing information about the trial to a prospective subject and allows for an informed decision about participation in the study. All subjects (or their legally acceptable representative) must read, sign, and date a consent form before entering the study, taking study drug, or undergoing any study-specific procedures. Consent materials for subjects who do not speak or read English must be translated into the subjects' appropriate language.

The informed consent form must be revised whenever important new safety information is available, whenever the protocol is amended, and/or whenever any new information becomes available that may affect participation in the trial.

A copy of the informed consent will be given to a prospective subject for review. The attending physician, in the presence of a witness if required by the IRB, will review the consent and answer questions. The prospective subject will be told that being in the trial is voluntary and that he or she may withdraw from the study at any time, for any reason.

# 13.3 Privacy and Confidentiality

A subject's privacy and confidentiality will be respected throughout the study. Each subject will be assigned a sequential identification number, and these numbers rather than names will be used to collect, store, and report subject information.

# 14. Publication Policy

The CIT policy on the publication of study results will apply to this trial.

# Appendix 1. Schedule of Events for Extended Follow-up

		SC	Local Visits 			On-Site Visit					
Visit schedule based on anniversary of	Timing					Anniversary					
last islet transplant in CIT parent study;	Timing	30			0	of Final					
visit schedule repeats each year.			3	6	9	Islet					
	0	month	month	month	Transplant						
Y7' '4 YA7' 1 / '4'	0	See MOP for Table of Vis									
Visit Window (specified	- 90	±14	±14	±14	± 30						
GENERAL ASSESSMENTS Informed Consent X											
Informed Consent											
Evaluate Inclusion/Exclusion Criteria Physical Exam	X X 				X						
	X 	Х	X	X	X						
AE /Hypoglycemic Events/Toxicity Asses Calculated GFR	$X^2$	Λ	Λ	Λ	X						
	$X^2$	V	V	V							
Insulin use Uring programmy test (females)		Х	X	X	X 						
Urine pregnancy test (females) X LOCAL LABORATORY ASSESSMENTS											
CBC (WBC + Diff & Plat) 	X  X X X X										
Chemistry 	X 	X	X	X	X						
Lipids 			Д	Λ	Λ	X					
Lipids		X 	2	(t :							
Alloantibody	Collect 3 months after immunosuppressive medication is stopped following graft failure.										
CENTRAL LABORA	ATORY/M	ETABOI	LIC ASSE	ESSMENT	ΓS						
HbA1c 						X					
Fasting serum gluc/c-pep & serum creating	ine 	X 				X					
MMTT 		X 				X					
CARDIO	VASCULA	R ASSES	SSMENT	S							
Carotid intimal thickness (IMT)			Collect at 5 years post-initial-islet transplant visit in subjects who completed the baseline carotid IMT assessment in their CIT parent study.8								
IMMUN	NOSUPPR	ESSION LEVELS									
Blood Trough Levels (if applicable) 		X 	X	X	X	X					
		SC	Local Visits  On-Site Visit								
Visit schedule based on anniversary of						Anniversary					
last islet transplant in CIT parent study;	Timing					of Final					
visit schedule repeats each year.			3	6	9	Islet					
y			month	month	month	Transplant					
	Visit #	0	See N	1OP for T	able of Vis	sit Numbers					
Visit Window (specified	- 90	±14	±14	±14	± 30						
MECHANISTIC ASSAYS - University of Pennsylvania Sub-Study  Only											
Autoantibody 			X		X						
Immunophenotyping 			X		X						
Cytokine profiling 			X		X						
Glucose-potentiated arginine 					X						
	RCHIVED	SAMPL	ES								
Serum						X					

<sup>1 These visits are performed locally but can be done on site if preferred.

<sup>2 Only collect if screening is ≥ 90 days since final parent study visit. Otherwise, results from final parent study visit should be used for screening (Visit 0).

<sup>3 Also collect AE assessment at time of premature study termination, if applicable.

<sup>4 Subjects must record insulin usage for 7 consecutive days within the visit window.

<sup>5 Also collect as clinically indicated.

<sup>6 Chemistry includes: Sodium, albumin, magnesium, chloride, potassium, alk phosphatase, total bilirubin, CO2, creatinine, ALT (SGPT), BUN, gamma GT, glucose, AST (SGOT), calcium, phosphorus

<sup>7 Do not collect after confirmed graft failure.

<sup>8 For those subjects who missed CIMT collection at the 5-year time point, collect at the next available opportunity.

<sup>9 These visits are performed locally but can be done on site if preferred.

 Please refer to CIT07 Protocol Appendix 6 for details on the University of Pennsylvania Sub-Study.

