## 4.1.2 Secondary Endpoints

Secondary endpoints include the following:

- Serum creatinine and calculated eGFR at each annual study visit
- Incidence of serious adverse events during the 12-month period preceding each annual study visit
- Insulin requirements during a one-week period preceding each annual study visit
- Incidence of severe hypoglycemic events during the 12-month period preceding each annual study visit
- HbA1c levels at each annual study visit
- All causes of mortality
- Presence of alloantibody after graft failure, in the absence of immunosuppression

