## 10.1.2 Secondary Endpoints

Insulin usage will be estimated from the one-week self report values. Estimates of population means and confidence intervals for those means will be reported for each follow-up visit. Linear mixed models methods will be used to describe the profile of change with time.

Numbers of severe hypoglycemic events will be estimated from the self report values obtained at each follow-up visit. Estimates of population means and confidence intervals for those means will be reported for each follow-up visit. Linear mixed models methods with appropriate likelihood functions will be used to describe trends with time.

HbA1c and serum creatinine levels will be measured at central laboratories at study entry and at the annual follow-up visit. GFR will be estimated using the updated CKD-EPI method. Estimates of population means and confidence intervals for those means will be reported for each follow-up visit. Linear mixed models methods will be used to describe trends with time.

Incidence of serious adverse experiences will be tabulated by body system and MeDRA code.

Life table methods will be used to estimate mortality rates.

The overall incidence of alloantibody conversion will be reported as a rate per 100 days of follow-up. A 95% confidence interval for the rate will be computed using boot-strap methods.

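### CIT08 stops HbA1c at confirmed graft failure although it is an annual endpoint for all subjects, and the laboratory source for post-failure creatinine is left in conflict

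*Protocol*

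**What the plan says.** All of this concerns CIT08, the extended follow-up protocol appended to CIT-05.

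- **Endpoints.** Section 4.1.2 lists "HbA1c levels at each annual study visit" and "Serum creatinine and calculated eGFR at each annual study visit". Neither is limited to the time while the graft functions.
- **Analysis.** Section 10.1.2 states: "HbA1c and serum creatinine levels will be measured at central laboratories at study entry and at the annual follow-up visit". It adds "GFR will be estimated using the updated CKD-EPI method", promises population means with confidence intervals at each visit, and says "Linear mixed models methods will be used to describe trends with time".
- **Schedule.** In Appendix 1, three central rows carry footnote 7: HbA1c, the combined fasting glucose, C-peptide and creatinine sample (its label reads "Fasting serum gluc/c-pep & serum creating", with the last word broken across the line), and the MMTT. Footnote 7 is: "Do not collect after confirmed graft failure".
- **Text on graft failure.** Section 7.2 says subjects with confirmed failure do not complete metabolic assessments. The graft-failure entry under Study Definitions says only that they need not.
- **Status of these subjects.** Graft failure is not among the withdrawal reasons in section 6.1, and section 7.2 follows subjects to the study end date.

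**The concern.** The endpoint and analysis sections promise an annual value for every subject in follow-up, and the schedule withholds it from those whose grafts have failed. For HbA1c, collection stops because of low C-peptide, the marker of lost graft function. As failures accumulate, the annual mean is taken over a shrinking, selected group while still being called a population mean. A steady or improving HbA1c curve could then reflect who is left rather than how the whole cohort fares.

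The mixed model helps only in part. It keeps each subject's pre-failure values, but beyond failure it must extrapolate from them, and there are almost no post-failure observations against which to check that extrapolation.

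For kidney function, the analysis text names central creatinine, and central creatinine stops at the same moment.

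**Working it through.** CIT08 gives no sample-size or precision figure for these endpoints, so there is nothing to reproduce. The check compares the schedule with the endpoints, and then illustrates the size.

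**Step 1. What continues after confirmed failure (Appendix 1 and its footnotes)**

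| Item | Footnote 7? | After failure |
|---|---|---|
| HbA1c (central) | yes | stops; no other row supplies it |
| Fasting glucose, C-peptide and creatinine (central) | yes | stops |
| MMTT | yes | stops |
| Local chemistry, which includes creatinine (footnote 6) | no (footnotes 5 and 6 only) | continues quarterly and annually |
| "Calculated GFR" | none visible | probably continues annually |

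The label of the last row runs together with the adverse-event row in the text as read, and no marker for footnote 3, which belongs to adverse-event assessment, is visible there. A missing marker on that line is therefore weak evidence. The chemistry row is intact and carries the argument.

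**Step 2. HbA1c**

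Let m be the mean HbA1c in subjects with working grafts, f the share of followed subjects whose grafts have failed, and d the amount by which their mean exceeds m.

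- All-subject mean = (1 − f)·m + f·(m + d) = m + f·d
- Observed mean = m
- Observed minus all-subject mean = −f·d

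CIT08 gives neither f nor d, so both are assumed:

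| f | d = 0.5 | d = 1.0 | d = 2.0 |
|---|---|---|---|
| 10% | −0.05 | −0.10 | −0.20 |
| 25% | −0.125 | −0.25 | −0.50 |
| 40% | −0.20 | −0.40 | −0.80 |

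With about 75 subjects, these shares correspond to about 8, 19 and 30 failures.

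The one figure in the documents that bears on f is in CIT-05 section 1.5.4, which cites C-peptide production in as many as 80% of recipients after 5 years. That leaves at least about 20% without it. At f = 20%, the shift is 0.20 × 0.5 = 0.10 to 0.20 × 2.0 = 0.40 points. The figure comes from a cited cohort, not from CIT08.

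**Step 3. Creatinine and eGFR**

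Section 4.1.2 names no laboratory; section 10.1.2 names the central one. Two readings follow.

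- If only central values are analysed, subjects with failed grafts leave the renal trend although their local creatinine is on file.
- If local values are substituted, the laboratory changes exactly at graft failure. Any offset between laboratories is then confounded with the effect of losing the graft.

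The protocol does not say which creatinine feeds eGFR after failure.

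**The case against.** The strongest defence is that the restriction is deliberate. Section 4 describes participants who still have graft function, section 1.4.3 gives the benefit as information on how long and how well grafts work, and the stop is stated openly in three places. HbA1c while the graft functions is a legitimate target. That stands as a possible intention, but the plan does not carry it through. The inclusion criteria in section 3.1 do not require graft function, and neither 4.1.2 nor 10.1.2 makes these endpoints conditional on it.

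It is also fair to say that some HbA1c values may be drawn once a graft has in fact failed. HbA1c and the MMTT share the annual visit, and the core-laboratory result takes up to 72 hours, so the HbA1c at the visit that confirms failure would already have been taken. The means therefore describe essentially, not strictly, only working grafts.

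The size is not grounded in trial data. Even the sign of d is an assumption: CIT-05 section 1.3.1 notes that HbA1c can be below 7% in patients with chaotic control.

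A reader might infer that CIT08 stops collecting kidney-safety data once a graft fails, or that these subjects are dropped. The documents do not support either. Local creatinine continues, renal insufficiency remains a recorded adverse event (section 8.2.1), and serious adverse events, severe hypoglycemia, insulin use and mortality are still followed. Alloantibody is assessed after failure once immunosuppression has stopped.

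**Conclusion.** The HbA1c point holds. As written, the schedule cannot deliver the endpoint in 4.1.2 or the analysis in 10.1.2, and the annual means increasingly describe subjects with functioning grafts. Under the assumed ranges the shift is 0.05 to 0.80 points. The upper end needs 40% failed and a 2-point difference, and nothing in the documents supports that combination.

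The renal point holds only as a conflict of source. Post-failure kidney data exist, but the analysis text points to a central sample that is no longer drawn.

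The contradiction itself does not depend on the assumed values; only its size does. It affects secondary, descriptive endpoints of CIT08 and leaves the CIT-05 primary endpoint and analysis untouched. It should be corrected because the repair is simple and the missing values cannot be recovered later.

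**What to change.** 1. In Appendix 1, remove footnote 7 from HbA1c and from central serum creatinine. Separate creatinine from the combined fasting row, and keep the footnote on the MMTT and on fasting glucose and C-peptide.
2. Align section 7.2 and the graft-failure definition, so that the metabolic assessments that end at failure no longer include HbA1c.
3. In section 10.1.2, report annual means for all subjects and separately by graft status.
4. If central creatinine is not resumed, state in 10.1.2 that local creatinine feeds eGFR after failure, and report the change of laboratory with the trend.

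If HbA1c is meant to be described only while the graft functions, the minimum repair is to say so in 4.1.2 and 10.1.2 and stop calling the results population means. That removes the contradiction but still leaves HbA1c after graft loss unknown.

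The cost is one HbA1c and one creatinine sample a year per subject with a failed graft, at an annual visit where local blood is already drawn.
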